10 MONITORING SUBJECTS AND CRITERIA FOR WITHDRAWAL

10.1 Patient Withdrawal and Termination Criteria.

Subjects will be informed that they may withdraw or be excluded from the study at any time. Our intention is to maintain stable doses of immunosuppression and antimalarials for the

duration of the trial. On occasion, doses are adjusted to treat SLE activity. While not ideal, we anticipate that over the duration of 8 months, outside providers may want to adjust or add new immunosuppressive therapy. In the event of these changes, each of these instances will be reviewed by the Principal Investigator to determine continuation or withdrawal from the trial to maintain scientific integrity.

The following conditions will require the discontinuation of study agent:

1. Subjects may voluntarily withdraw at any point
2. Flares not responding to the treatment above or if, in the opinion of the responsible investigator, the subject needs immediate immunosuppressive therapy that is not allowed in the protocol
3. Any Grade 4 adverse event that is unexpected and at least possibly, probably or definitely related to study drug
4. More than 1 “no-show” for a visit
5. Becoming pregnant after baseline visit. The subject will be followed for the outcome of the pregnancy.
6. Any other reason that, in the opinion of the responsible investigator, poses unacceptable risk to the subject.
7. Nevertheless, LFTs will be monitored on all patients at each study visit and those patients with LFTs >2x upper limit at Screening visit will be excluded. If during the trial, LFTs increase to > than 3x fold the upper limit of normal (ULN), levels will be rechecked within 36 hours and if elevation >3 ULN persists and there are not alternative etiologies, therapy will be discontinued. If LFTs are elevated >2 but < 3x ULN (after confirming within 48 hours), we will investigate etiology of liver enzyme elevation and cautiously reinstate therapy if alternative etiology is found. For patients with NAFLD that are enrolled, based on recent clinical trials that have been published (Cusi K et al. Annals of Internal Medicine 2016) assessing the role of long-term pioglitazone treatment for nonalcoholic steatohepatitis, we will include only patients that have LFTs < 3 times ULN. If there is an increase to >3 times ULN once study drug starts during monitoring (confirmed within 24 hours), drug will be stopped.

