10.2 Study Completion Criteria

A subject is considered to have completed the study when he/she has completed 8 months in the trial and received both treatment arms of the study. Enrolled subjects who withdraw from the trial prior to receiving study agent or who only complete one arm will be replaced; however, patients who complete only one arm will still be included in analysis.

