11 DATA ANALYSIS

The study measures the primary and secondary outcome variables at 4 time periods in each subject. We will begin with a univariate investigation of the outcomes to check for outliers and distributional properties followed by an assessment for carryover effects. The analysis of the study will be conducted using a 2-period cross-over model by comparing matched pair differences for the subjects in the first sequence with those in the second sequence. We expect this analysis will indicate no difference between the groups. If we find no carry over effect the modeling will continue without controlling for sequence. If we do find a sequence effect we will account for it in our models. The analysis will be based on a repeated measures analysis accounting for treatment and period effects and incorporating the two baseline measures. We will use a generalized linear model and a Generalized Estimating Equations (GEE) framework with two dummy variables, one indicating treatment condition and the other indicating the baseline condition (the omitted or the reference condition is Placebo). We will use an unstructured covariance matrix and robust standard errors. The primary parameter of interest is the regression coefficient for the treatment condition (a contrast between the placebo and pioglitazone). This approach is attractive because it can handle non-normal and categorical outcomes. The analysis is robust to model mis-specification¹⁵⁴.

The approach used in testing the hypothesis under the three specific aims will be similar. For Specific Aim 1, we will perform a separate analysis for each outcome variable: CAVI/Sphygmocor, PAT and FDG/CT. We will also perform secondary analysis using serum and cellular CV biomarkers. Our first analysis will be a randomization based analysis with no

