covariates other than treatment and period effects. There are several confounding variables, especially medications that could contribute towards the variation in the outcome. We will expand the regression models by including them as predictors. If the number of confounding variables is large, we will use investigate a propensity score matching analysis. For Specific Aim 2, we will define a dichotomous clinical endpoint measuring lupus disease activity. Patients achieving an improvement of the SLEDAI-2K by 20%, a significant improvement in PGA and the absence of a BILAG 2004 A or B flare will be considered to have improved. Others will be defined as not having improved. The analysis for this score will be similar to the one proposed for Specific Aim 1. A GEE model will be used to assess treatment differences. We will also investigate the separate effects of each of these measures. The same approach used in Aim 1 will be taken for confounding variables using regression or propensity score adjustment. We will begin the investigation of Aim 3, assessment of innate and adaptive immune abnormalities in SLE, with a graphical analysis of the variables. We use multivariate methods to determine good summary measures of the various factors and compare the two treatments using the same models as defined for Aims 1 and 2.

Our primary analysis will be performed as an intent-to-treat analysis. If the subjects providing complete data are systematically different from those who dropped out, then the estimates based only on completers will be biased. We will investigate adjusting for differences in the populations who are completers and noncompleters and will consider multiple imputation to impute the missing values. Before the database is locked and final analysis performed, violations will be assessed on a case-by-case basis by the PI to determine if the medication change was such that it would adversely affect the study results. If changes may adversely affect data interpretation, subjects will be dropped from final analysis. A post hoc analysis of disease activity, measured by SLEDAI-2K, will be adjusted for burst steroids in excess of that permitted by the protocol. Analysis of prednisone doses, daily and cumulative will also be included.

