11.1 Power and Sample Size

We arrived at sample size based on previous publications for arterial stiffness and vascular dysfunction observed in SLE^{92, 101-103} as well as on our recently completed RA trial. To achieve this sample size, we will be recruiting 100 patients, assuming a 20% or more dropout rate (see below). The actual analysis will be more powerful and will use data on all subjects including those who provide partial information. Based on our previous experience with the CV lupus cohort and on published literature on cross-over designs using pioglitazone to measure CV markers in other populations, we estimate our dropout rate to be between 3-20%. We have then projected a 20% drop-out rate that includes both drop-outs, as well as the few people who are deemed protocol violators because of significant changes in immunosuppressive or vascular medications. This sample will give us power to detect moderate standardized differences for the other variables measured in this study. As this is a “proof of concept” study, we estimate it is

important to detect at least moderate differences in outcome for them to be clinically meaningful.

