This study includes pregnancy information as safety data and pregnancies will be recorded if they begin any time after enrollment. Information about any pregnancy should be reported promptly to the NIH NIAMS/NIDDK IRB, NIAMS Clinical Director, and DSMC on the same timeline as a SAE. All pregnancies identified during the study must be followed to conclusion and the outcome of each must be reported. The investigator should be informed immediately of any pregnancy in a study subject or a partner of a study subject. A pregnant subject should be instructed to stop taking study medication. The investigator will refer patient to High-risk Obstetrics for counseling and follow-up. Pioglitazone has a pregnancy risk factor Category C; there are no adequate and well controlled studies in pregnant women. Animal studies show increased rates of post-implantation loss, delayed development, reduced fetal weights, and delayed parturition at doses 10 to 40 times the maximum recommended human dose (Label, 2013). Monitoring of the pregnant subject should continue until the conclusion of the pregnancy, and a follow-up Pregnancy Monitoring form detailing the outcome of the pregnancy should be submitted to the IRB. When possible, similar information should be obtained for a pregnancy occurring in a partner of a study subject. Information requested about the delivery will include:

- Subject's enrollment ID
- Gestational age at delivery

- Birth weight, length, and head circumference
- Gender
- Appearance, pulse, grimace, activity, and respiration (APGAR) score at 1 minute, 5 minutes, and 24 hours after birth, if available
- Any abnormalities.

Should the pregnancy result in a congenital abnormality or birth defect, an SAE also must be submitted to the NIH NIAMS/NIDDK IRB using the SAE reporting procedures described above.

12.3.18 Lost to follow up patient reporting:

After three attempts to contact the patient via phone, a certified letter will be sent to notify him or her that they have been withdrawn from the study.

12.3.19 Stopping Rules:

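### Section 12.3.18 withdraws a patient from the study after three phone attempts, with no minimum period and no later outcome visits, so a patient only briefly out of contact can lose crossover endpoints

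*Combined protocol and SAP*

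**What the plan says.** Section 12.3.18 (Lost to follow up patient reporting) is one sentence. The trigger is "After three attempts to contact the patient via phone". The consequence is that "a certified letter will be sent to notify him or her that they have been withdrawn from the study". The sentence gives no spacing between calls, no minimum period, no second contact route before withdrawal and no route back.

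Section 10.1 has a separate list, introduced by "The following conditions will require the discontinuation of study agent". Its item 4 reads "More than 1 “no-show” for a visit". Neither section refers to the other.

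On the analysis, section 11 states "Our primary analysis will be performed as an intent-to-treat analysis" and describes the crossover comparison as "using a 2-period cross-over model by comparing matched pair differences". It acknowledges that estimates from completers alone will be biased if dropouts differ systematically, and says multiple imputation will be considered. Section 10.2 replaces patients who complete one arm but adds that "patients who complete only one arm will still be included in analysis". Section 11.1 says the analysis "will use data on all subjects including those who provide partial information".

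**The concern.** A crossover trial draws its precision from having each patient's outcome at the end of both treatment periods. Section 12.3.18 can remove a patient before those outcomes are taken, by an administrative rule that depends on phone contact. It does not depend on the patient's wishes, on safety or on ability to attend. Someone who is travelling, in hospital or without a working phone for a short time meets the trigger just as someone who has left for good does.

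Two things are at stake. The first is information: the patient's within-person treatment contrast is lost. The second is bias. Patients who cannot be reached may be ill, so the loss may be related to outcome or treatment. An intent-to-treat analysis is best protected by continuing to collect outcomes from everyone randomised who is willing to give them, and the plan provides no way to do so once the letter has gone out.

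**Working it through.** **Inputs**

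- Outcome schedule (Table 3, sections 9.5.1 and 9.5.3): vascular function studies, SLEDAI-2K, BILAG 2004 and PGA at baseline and months 3, 5 and 8.
- Months 1 and 6 (section 9.5.2): safety visits with no efficacy endpoint. Bloods may be drawn locally and adverse events taken by phone.
- Other scheduled calls (section 9.5.1): one before the dose increase and one 1 to 2 weeks after it.
- Study drug (section 10.4 and Table 3): a 300-capsule vial at baseline and again at month 5, with accountability at months 3 and 8.
- Post-withdrawal outcome visits: none described.

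**Step 1. What is lost, by when the rule is applied**

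| Withdrawal falls | Outcomes in hand | Outcomes lost | Left for the treatment contrast |
|---|---|---|---|
| Before month 3 (dose calls, month 1) | baseline | 3, 5, 8 | no end-of-treatment outcome |
| Between months 3 and 5 | baseline, 3 | 5, 8 | one period only |
| Between months 5 and 8 (including month 6) | baseline, 3, 5 | 8 | one end-of-treatment outcome only |
| At month 8 | baseline, 3, 5 | 8, if the patient would return within the window | little further loss due to the rule |

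In the first three rows the patient has no pair of end-of-treatment outcomes. In the first row section 10.2 is also silent: it covers patients who withdraw before receiving study agent and those who complete one arm, but not those who took study agent and completed neither.

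**Step 2. The two rules side by side**

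| | 12.3.18 | 10.1 item 4 |
|---|---|---|
| Trigger | three phone attempts | more than one missed visit |
| Stated consequence | withdrawal from the study | discontinuation of study agent |

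A patient with one missed visit who cannot be reached does not meet 10.1 item 4 but does meet 12.3.18. Because 12.3.18 does not mention a missed visit, unanswered scheduled calls could meet it with no missed visit at all. The triggers and consequences differ, so both rules can be applied without conflict. What is missing is any statement of how they fit together, and any separation of stopping drug from leaving follow-up.

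**Step 3. Size**

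The only number this rule touches is the dropout allowance. Section 11.1 recruits 100 and assumes 20% or more dropout; section 8 aims for up to 75 completers.

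- 75 / (1 − 0.20) = 93.75, rounded up to 94, which is not 100.
- 75 / (1 − 0.25) = 100.
- 80 / (1 − 0.20) = 100.

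So 100 fits 75 completers with 25% loss, consistent with 20% or more. Losses under 12.3.18 fall inside that allowance, but no share is attributed to loss of contact.

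Section 11.1 gives no alpha, power, effect size or SD, so the plan's power cannot be reproduced. As an illustration only, assume two-sided alpha 0.05, 80% power and 75 complete pairs. The detectable difference is (1.9600 + 0.8416) / √75 = 2.8016 / 8.6603, about 0.323 SD of the within-patient difference. If m pairs are lost, not replaced and contribute nothing, power is Φ(0.323 × √(75 − m) − 1.96):

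- m = 5: 77.2%
- m = 10: 74.2%
- m = 15: 70.7%

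These figures show what a lost pair costs. They do not estimate how many pairs the phone rule would cost, because the documents give no basis for m.

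**The case against.** The strongest reply has four parts.

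**No contradiction.** A reader might infer that 12.3.18 overrides a tolerance of one missed visit granted in 10.1. The documents do not support that. Item 4 counts missed visits and sits in a list about study agent; 12.3.18 concerns patients who cannot be reached. This part stands. What remains is that the two rules are not reconciled.

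**Silence is not a rule.** The text does not say that the calls follow a single missed visit, that they are made close together, or that a returning patient is refused. It does not give the letter's full wording, and section 12.4 refers to a Manual of Procedures that may contain contact procedures. This stands as a limit: the text permits a quick withdrawal but does not state one. It does not remove the point, because the protocol's operative sentence makes withdrawal the outcome and describes the letter only as notice of it.

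**Mitigation exists.** Data already collected are kept, partial data are used, patients may be replaced, adjustment and imputation will be considered, and the local-laboratory and phone option makes months 1 and 6 easier to complete. All of this is true and limits the damage. Replacement restores numbers but not the missing outcomes of the patient who was randomised, and it does not correct bias if loss of contact is informative. Imputation is only to be considered, and it rests on assumptions that an observed month 3 or month 8 value would not need.

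**No measurable effect.** A reader might assume a chance per visit of losing contact, multiply it over the five post-baseline visits and quote a percentage withdrawn. The documents give no such rate. The result would also depend on independence between visits and on which visits can still cost a later outcome. Comparing it with the 10.1 rule at the same rate would not be like for like, since a missed visit is a more common event than a missed visit with three unanswered calls. No percentage is offered here.

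**Conclusion.** The point holds in a limited form. As written, 12.3.18 turns three phone attempts into study withdrawal, with no minimum period and no provision for outcomes afterwards. Applied as written, it can forfeit end-of-period outcomes that an intent-to-treat crossover analysis needs, from patients who might have returned in time to give them. The existing safeguards reduce the loss of numbers but restore neither the within-patient contrast nor protection against informative loss.

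The size is unknown. The conclusion rests on two assumptions: that the site follows the sentence as it stands, and that some patients who meet the trigger would return before month 3, 5 or 8. It does not rest on any conflict with 10.1. It deserves correction because the remedy is cheap and prevents missing data that would otherwise have to be modelled.

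**What to change.** Reword 12.3.18 so that:

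- the certified letter is a further contact attempt, asking the patient to contact the site and return unused study drug;
- the visit concerned is recorded as missed;
- the remaining scheduled outcome assessments at months 3, 5 and 8 stay open to a patient who returns;
- loss to follow-up is assigned only when the month 8 window closes without contact.

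Reconcile 12.3.18 with 10.1, so that what ends follow-up is stated separately from what stops study agent. Which condition should stop study agent is a clinical decision for the investigators, and nothing is proposed on it here.

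The cost is about one paragraph of protocol text and some coordinator time. No visit or procedure is added.

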12.3 Compliance with Good Clinical Practices

This trial will be conducted in compliance with the protocol, current GCPs recommended by the International Conference on Harmonization (ICH) and the applicable regulatory requirements for participating institutions. These include the tenets of the Declaration of Helsinki and review and approval by the appropriate ethics review committee or IRBs of participating organizations.

12.4 Data Safety and Monitoring

The study will be conducted according to Good Clinical Practice (GCP) guidelines, the Manual of Procedures (MOP), U.S. 21 CFR Part 50 – Protection of Human Subjects, 21CFR312 subpart D and Part 56 – Institutional Review Boards.

12.5 Data Safety Monitoring Committee

The NIAMS DSMC will have safety oversight responsibilities for the study. DSMC will be comprised of 3 members after discussion with NIAMS Clinical Director. The DSMC Chair will not be affiliated to NIAMS.

Approximately twice a year (as mentioned in section 11.2), the DSMC will review data related to enrollment progress, study implementation, subject safety, and protocol violations. The CTDB will generate reports that compile all newly submitted and accumulated AEs, SAEs, toxicities, pregnancies, and concomitant medications. Subsequent review of periodic reports will be performed by the Principal Investigator.

The DSMC will also consider current information from other sources on the biology of the disease and the subject population under study. Based on these reviews, the DSMC will make recommendations to the Principal Investigator and the NIAMS Clinical Director concerning the continuation, modification, or termination of the study. The DSMC will also meet ad hoc if relevant issues arise that require committee review.

The Principal Investigator will be responsible for reporting incidents of non-compliance to the NIH IRB (in compliance with regulations on the protection of human subjects and institutional policy and procedures) and responsible for securing compliance.

Clinical monitoring for this study will be based on a clinical monitoring plan developed by Leidos Biomedical Research, Inc., Clinical Monitoring Research Program, Clinical Trials Management team in collaboration with the principal investigator. The purposes of the clinical monitoring activities are:

- 1) To verify the existence of signed informed consent documents and documentation of the ICF process for each monitored subject;
- 2) To verify the prompt and accurate recording of all monitored data points, and prompt reporting of all SAEs;
- 3) To compare abstracted information with individual subjects' records and source documents (subjects' charts, laboratory analyses and test results, physicians' progress notes, nurses' notes, and any other relevant original subject information); and
- 4) To help ensure investigators are in compliance with the protocol.

The monitors also will inspect the clinical site regulatory files to ensure that regulatory requirements (Office for Human Research Protections-OHRP) and applicable guidelines (ICH-GCP) are being followed.

During the monitoring visits, the investigator (and/or designee) and other study personnel will be available to discuss the study progress and monitoring visit.

The Clinical Monitoring Plan will specify the frequency, procedures, and levels of monitoring activities. Some monitoring activities will be performed remotely (e.g., review of regulatory documents), while others will take place on site (e.g., verification of study databases against source documentation).

The staff from Leidos Biomedical Research Inc. CMRP/CTM will conduct the monitoring activities and provide the follow-up letters describing the findings. The frequency of reporting for monitoring activities will be specified in the monitoring plan. The Principal Investigator will receive copies of the final follow-up letters.

12.6 Research Use, Storage, and Disposition of Human Samples If, Specimens, or Data

12.6.1 Data Collection

Study staff will complete electronic case report forms (eCRFs) that will be compiled and stored in a computerized central database CTDB. Security of the database system is maintained through an application firewall, military grade encryption and SSL certificates, removal of personal identifiers consistent with HIPAA requirements (45 C.F.R. 164.514(a),(b)&(c)).

Research samples collected from subjects consenting to this protocol will be stored in locked secure freezers belonging to NIAMS. The freezers are located in Building 10 at the NIH. Samples will be kept indefinitely unless there is a significant justification for destroying them. The Principal Investigator will report to the Institutional Review Board (IRB) the loss or destruction of samples collected under this protocol.

All samples will be coded and will not have personal identifiers. The codes for identifiers will be contained in a secure electronic database (CTDB) and a subject code log that is maintained in secure research files. An electronic record log with identifiers of all collected research specimens will be kept. These will be stored in either research charts or on secure NIH computers.

If coded samples are shared with collaborators within or outside the NIH in the future, tech transfer agreements, MTAS or CRADAS will be obtained and an amendment will be submitted to IRB to describe the nature of this collaboration. Currently, we do not have any planned collaborations. Samples will be stored in the NIAMS and may be used by the investigators in this proposal for studies in the pathogenesis of SLE. Approval from the IRB will be obtained prior to any research use of stored samples beyond the scope of this study.

All patient samples will be coded and used for research purposes without sharing identifying information and all collaborators will follow federal rules for clinical research.

The investigators will retain all study-related records for at least 3 years after discontinuation of the study. Some of the research data might be maintained indefinitely for research purposes. Research records and all source documents will be kept in locked cabinets or rooms, and computer research databases will be stored in a secure, password-protected environment, per standard NIH policies. Only study investigators and participating research personnel will have access to the data.

The site investigators are required to keep accurate records to ensure the conduct of the study is fully documented. The period of record retention should be consistent with the record retention

policies of the sponsoring agency or applicable regulatory agencies. Medical and research records will be maintained in the strictest confidence. However, as a part of the quality assurance and legal responsibilities of an investigation, Principal investigator must permit authorized representatives of the IND sponsor (if applicable), Leidos, CTDB at the NIH and health authorities to examine (and when required by applicable law, to copy) clinical records for the purposes of quality assurance reviews, audits, and evaluation of the study safety and progress. Unless required by the laws permitting copying of records, only the coded identity associated with documents or other subject data may be copied (obscuring any personally identifying information). Authorized representatives as noted above are bound to maintain the strict confidentiality of medical and research information that may be linked to identified individuals. Participating sites will normally be notified in advance of auditing visits.

Study staff will complete electronic case report forms (eCRFs) via a web-based electronic data capture (EDC) system (Clinical Trials Database, CTDB) that is compliant with Part 11 Title 21 of the Code of Federal Regulations. Subject's electronic medical records in the Clinical Research Information System (CRIS) will be used as source documents for these eCRFs.

CRFs and subject questionnaire data will be kept in the CTDB database.

The data will be further validated via a series of manual edit checks, and all relevant data queries will be raised and resolved on an ongoing basis. Complete, clean data will be frozen to prevent further inadvertent modifications. All discrepancies will be reviewed and any resulting queries will be resolved with the investigators and amended in the database. All elements of data entry (i.e., time, date, verbatim text, and the person performing the data entry) will be recorded in an electronic audit trail to allow all data changes in the database to be monitored and maintained in accordance with federal regulations.

